Appendix B

Lab values-Triglyceride level (mg/dl) (within 3 months); n (%)	181 (8.4%)	190 (8.8%)	-0.01	20 (0.4%)	28 (0.5%)	-0.01	N/A	N/A	201 (2.6%)	218 (2.8%)	-0.01
Lab values-Triglyceride level (mg/dl) (within 6 months); n (%)	316 (14.7%)	351 (16.3%)	-0.04	34 (0.6%)	43 (0.8%)	-0.02	N/A	N/A	350 (4.5%)	394 (5.0%)	-0.02
Lab result number- HbA1c (%) mean (only 2 to 20 included)v4	258	259		41	47		N/A	N/A	299	306	
...mean (sd)	6.67 (1.56)	6.63 (1.56)	0.03	7.09 (1.30)	7.13 (1.71)	-0.03	N/A	N/A	6.73 (1.53)	6.71 (1.59)	0.01
...Missing; n (%)	1,895 (88.0%)	1,894 (88.0%)	0.00	5,634 (99.3%)	5,628 (99.2%)	0.01	N/A	N/A	7,529 (96.2%)	7,522 (96.1%)	0.01
Lab result number- BNP mean v2	23	29		2	3		N/A	N/A	25	32	
...mean (sd)	65.94 (82.23)	155.95 (239.40)	-0.50	38.70 (3.11)	75.00 (68.46)	-0.75	N/A	N/A	63.76 (82.23)	148.36 (235.92)	-0.48
...Missing; n (%)	2,130 (98.9%)	2,124 (98.7%)	0.02	5,673 (100.0%)	5,672 (99.9%)	0.04	N/A	N/A	7,803 (99.7%)	7,796 (99.6%)	0.02
Lab result number- BUN (mg/dl) mean v2	508	589		51	68		N/A	N/A	374.69 (839.77)	199.22 (4657.11)	0.03
...mean (sd)	16.85 (6.32)	16.63 (6.05)	0.04	3,939.06 (28,003.10)	1,780.81 (14,550.16)	0.10	N/A	N/A	559	657	
...Missing; n (%)	1,645 (76.4%)	1,564 (72.6%)	0.09	5,624 (99.1%)	5,607 (98.8%)	0.03	N/A	N/A	7,269 (92.9%)	7,171 (91.6%)	0.05
Lab result number- Creatinine (mg/dl) mean (only 0.1 to 15 included)v3	508	601		49	72		N/A	N/A	557	673	
...mean (sd)	0.97 (0.31)	0.94 (0.24)	0.11	1.01 (0.26)	0.96 (0.26)	0.19	N/A	N/A	0.97 (0.31)	0.94 (0.24)	0.11
...Missing; n (%)	1,645 (76.4%)	1,552 (72.1%)	0.10	5,626 (99.1%)	5,603 (98.7%)	0.04	N/A	N/A	7,271 (92.9%)	7,155 (91.4%)	0.06
Lab result number- HDL level (mg/dl) mean (only <=5000 included)v2	314	352		35	43		N/A	N/A	349	395	
...mean (sd)	53.71 (16.56)	52.98 (16.30)	0.04	46.42 (18.95)	48.02 (16.23)	-0.09	N/A	N/A	52.98 (16.83)	52.44 (16.31)	0.03
...Missing; n (%)	1,839 (85.4%)	1,801 (83.7%)	0.05	5,640 (99.4%)	5,632 (99.2%)	0.02	N/A	N/A	7,479 (95.5%)	7,433 (95.0%)	0.02
Lab result number- LDL level (mg/dl) mean (only <=5000 included)v2	318	351		32	41		N/A	N/A	350	392	
...mean (sd)	102.29 (35.24)	102.76 (39.24)	-0.01	100.14 (43.88)	102.63 (43.57)	-0.06	N/A	N/A	102.09 (36.15)	102.75 (39.76)	-0.02
...Missing; n (%)	1,835 (85.2%)	1,802 (83.7%)	0.04	5,643 (99.4%)	5,634 (99.3%)	0.01	N/A	N/A	7,478 (95.5%)	7,436 (95.0%)	0.02
Lab result number- Total cholesterol (mg/dl) mean (only <=5000 included)v2	320	354		35	44		N/A	N/A	355	398	
...mean (sd)	186.00 (39.30)	186.53 (44.31)	-0.01	179.03 (51.44)	184.27 (47.29)	-0.11	N/A	N/A	185.31 (40.69)	186.28 (44.70)	-0.02
...Missing; n (%)	1,833 (85.1%)	1,799 (83.6%)	0.04	5,640 (99.4%)	5,631 (99.2%)	0.02	N/A	N/A	7,473 (95.5%)	7,430 (94.9%)	0.03
Lab result number- Triglyceride level (mg/dl) mean (only <5000 included)v2	316	351		34	42		N/A	N/A	350	393	
...mean (sd)	141.37 (80.85)	145.40 (97.12)	-0.05	161.92 (102.42)	148.55 (81.44)	0.14	N/A	N/A	143.37 (83.26)	145.74 (95.72)	-0.03
...Missing; n (%)	1,837 (85.3%)	1,802 (83.7%)	0.04	5,641 (99.4%)	5,633 (99.3%)	0.01	N/A	N/A	7,478 (95.5%)	7,435 (95.0%)	0.02
Lab result number- Hemoglobin mean (only >0 included)	427	464		42	56		N/A	N/A	469	520	
...mean (sd)	13.45 (1.77)	13.33 (1.82)	0.07	3,417.04 (22,063.44)	2,673.48 (19,909.23)	0.04	N/A	N/A	318.25 (6544.44)	299.81 (6493.68)	0.00
...Missing; n (%)	1,726 (80.2%)	1,689 (78.4%)	0.04	5,633 (99.3%)	5,619 (99.0%)	0.03	N/A	N/A	7,359 (94.0%)	7,308 (93.4%)	0.02
Lab result number- Serum sodium mean (only >90 and <190 included)	495	574		47	67		N/A	N/A	542	641	
...mean (sd)	140.20 (2.66)	140.06 (2.68)	0.05	139.22 (3.38)	139.19 (2.55)	0.01	N/A	N/A	140.12 (2.73)	139.97 (2.67)	0.06
...Missing; n (%)	1,658 (77.0%)	1,579 (73.3%)	0.09	5,628 (99.2%)	5,608 (98.8%)	0.04	N/A	N/A	7,286 (93.1%)	7,187 (91.8%)	0.05
Lab result number- Albumin mean (only >0 and <=10 included)	472	522		42	55		N/A	N/A	514	577	
...mean (sd)	4.08 (0.39)	4.10 (0.36)	-0.05	3.91 (0.93)	4.02 (0.66)	-0.14	N/A	N/A	4.07 (0.46)	4.09 (0.40)	-0.05
...Missing; n (%)	1,681 (78.1%)	1,631 (75.8%)	0.05	5,633 (99.3%)	5,620 (99.0%)	0.03	N/A	N/A	7,314 (93.4%)	7,251 (92.6%)	0.03
Lab result number- Glucose (fasting or random) mean (only 10-1000 included)	491	568		50	71		N/A	N/A	541	639	
...mean (sd)	113.45 (43.92)	110.67 (37.41)	0.07	142.44 (59.71)	144.25 (99.21)	-0.02	N/A	N/A	116.13 (45.62)	114.40 (48.28)	0.04
...Missing; n (%)	1,662 (77.2%)	1,585 (73.6%)	0.08	5,625 (99.1%)	5,604 (98.7%)	0.04	N/A	N/A	7,287 (93.1%)	7,189 (91.8%)	0.05
Lab result number- Potassium mean (only 1-7 included)	507	592		48	64		N/A	N/A	555	656	
...mean (sd)	4.33 (0.42)	4.32 (0.42)	0.02	4.30 (0.44)	4.24 (0.40)	0.14	N/A	N/A	4.33 (0.42)	4.31 (0.42)	0.05
...Missing; n (%)	1,646 (76.5%)	1,561 (72.5%)	0.09	5,627 (99.2%)	5,611 (98.9%)	0.03	N/A	N/A	7,273 (92.9%)	7,172 (91.6%)	0.05
Comorbidity Scores											
CCI (180 days)-ICD9 and ICD10 v2											
...mean (sd)	2.79 (2.31)	2.78 (2.47)	0.00	1.74 (2.00)	1.69 (2.04)	0.02	2.57 (2.34)	2.53 (2.39)	2.30 (2.22)	2.26 (2.28)	0.02
Non-Frailty; n (%)	1,041 (48.4%)	1,027 (47.7%)	0.01	2,447 (43.1%)	2,383 (42.0%)	0.02	310 (3.8%)	252 (3.1%)	3,798 (23.9%)	3,662 (23.0%)	0.02
Frailty Score (mean): Empirical Version 365 days, v2	0.19 (0.06)	0.19 (0.07)	0.00	0.16 (0.05)	0.16 (0.05)	0.00	0.09 (0.07)	0.10 (0.07)	0.13 (0.06)	0.13 (0.06)	0.00
Healthcare Utilization											
Any hospitalization; n (%)	2,034 (94.5%)	2,011 (93.4%)	0.05	5,674 (100.0%)	5,675 (100.0%)	#DIV/0!	7,678 (95.2%)	7,733 (95.9%)	15,386 (96.8%)	15,419 (97.0%)	-0.01
Any hospitalization within prior 30 days; n (%)	1,966 (91.3%)	1,967 (91.4%)	0.00	5,661 (99.8%)	5,658 (99.7%)	0.02	7,617 (94.4%)	7,655 (94.9%)	15,244 (95.9%)	15,280 (96.1%)	-0.01
Any hospitalization during prior 31-180 days; n (%)	262 (12.2%)	247 (11.5%)	0.02	448 (7.9%)	415 (7.3%)	0.02	1,216 (15.1%)	1,052 (13.0%)	1926 (12.1%)	1714 (10.8%)	0.04
Internal medicine/family medicine visits; n (%)	1,920 (89.2%)	1,911 (88.8%)	0.01	4,445 (78.3%)	4,436 (78.2%)	0.00	7,824 (97.0%)	7,851 (97.3%)	14189 (89.3%)	14198 (89.3%)	0.00
Internal medicine/family medicine visits (30 days prior); n (%)	1,743 (81.0%)	1,723 (80.0%)	0.03	3,220 (56.7%)	3,134 (55.2%)	0.03	7,554 (93.7%)	7,574 (93.9%)	12517 (78.8%)	12431 (78.2%)	0.01
Internal medicine/family medicine visits (31 to 180 days prior); n (%)	1,375 (63.9%)	1,360 (63.2%)	0.01	3,520 (62.0%)	3,585 (63.2%)	-0.02	5,892 (73.1%)	5,955 (73.8%)	10787 (67.9%)	10900 (68.6%)	-0.02
Cardiologist visit; n (%)	1,530 (71.1%)	1,486 (69.0%)	0.05	1,416 (25.0%)	1,453 (25.6%)	-0.01	5,922 (73.4%)	5,904 (73.2%)	8868 (55.8%)	8843 (55.6%)	0.00
Number of Cardiologist visits (30 days prior); n (%)	1,393 (64.7%)	1,361 (63.2%)	0.03	1,000 (17.6%)	1,011 (17.8%)	-0.01	5,390 (66.8%)	5,362 (66.5%)	7783 (49.0%)	7734 (48.7%)	0.01
Number of Cardiologist visits (31 to 180 days prior); n (%)	405 (18.8%)	404 (18.8%)	0.00	619 (10.9%)	637 (11.2%)	-0.01	2,029 (25.2%)	2,030 (25.2%)	3053 (19.2%)	3071 (19.3%)	0.00
Electrocardiogram v2; n (%)	1,793 (83.3%)	1,843 (85.6%)	-0.06	2,747 (48.4%)	2,750 (48.5%)	0.00	7,025 (87.1%)	7,025 (87.1%)	11565 (72.8%)	11618 (73.1%)	-0.01
Use of glucose test strips; n (%)	28 (1.3%)	29 (1.3%)	0.00	46 (0.8%)	46 (0.8%)	0.00	98 (1.2%)	98 (1.2%)	172 (1.1%)	173 (1.1%)	0.00
Dialysis; n (%)	0 (0.0%)	0 (0.0%)	#DIV/0!	0 (0.0%)	0 (0.0%)	#DIV/0!	** (0.0%)	** (0.0%)	#VALUE!	#VALUE!	#VALUE!

Appendix B

number of different/distinct medication prescriptions	9.05 (5.56)	9.04 (5.50)	0.00	8.49 (5.04)	8.53 (5.59)	-0.01	9.74 (4.89)	9.85 (4.98)	9.20 (5.04)	9.27 (5.28)	-0.01
Number of Hospitalizations	1.16 (0.62)	1.17 (0.70)	-0.02	1.18 (0.52)	1.17 (0.48)	0.02	1.25 (0.72)	1.26 (0.68)	1.21 (0.64)	1.22 (0.62)	-0.02
Number of hospital days	5.88 (3.52)	5.78 (5.88)	0.02	5.05 (3.36)	4.99 (4.88)	0.01	6.38 (3.73)	6.32 (6.02)	5.84 (3.57)	5.77 (5.62)	0.01
Number of Emergency Department (ED) visits v3	1.58 (2.36)	1.60 (2.03)	-0.01	3.00 (4.68)	2.87 (4.74)	0.03	1.67 (1.95)	1.72 (2.10)	2.13 (3.24)	2.11 (3.29)	0.01
Number of Office visits	5.23 (4.60)	5.24 (4.55)	0.00	4.86 (4.49)	4.89 (4.50)	-0.01	13.55 (14.34)	13.53 (13.73)	9.32 (10.70)	9.32 (10.28)	0.00
Number of internal medicine/family medicine visits	11.10 (14.06)	9.98 (12.28)	0.08	5.68 (9.10)	5.56 (8.53)	0.01	12.71 (10.92)	11.84 (10.57)	9.98 (10.81)	9.35 (10.15)	0.06
Number of Cardiologist visits	2.39 (3.48)	2.36 (3.42)	0.01	0.64 (1.87)	0.63 (2.02)	0.01	2.81 (4.08)	2.87 (4.25)	1.98 (3.37)	2.00 (3.49)	-0.01
Number of electrocardiograms received v2	1.98 (2.14)	2.01 (2.00)	-0.01	0.83 (1.16)	0.83 (1.22)	0.00	2.02 (1.75)	2.03 (1.70)	1.59 (1.63)	1.60 (1.59)	-0.01
Number of HbA1c tests ordered	0.32 (0.65)	0.32 (0.64)	0.00	0.20 (0.51)	0.20 (0.50)	0.00	0.35 (0.66)	0.35 (0.65)	0.29 (0.61)	0.29 (0.60)	0.00
Number of glucose tests ordered	0.21 (1.51)	0.19 (0.99)	0.02	0.10 (0.52)	0.11 (0.78)	-0.02	0.14 (0.59)	0.14 (0.54)	0.14 (0.76)	0.14 (0.71)	0.00
Number of lipid tests ordered	0.47 (0.72)	0.50 (1.17)	-0.03	0.35 (0.72)	0.35 (0.70)	0.00	0.55 (0.71)	0.55 (0.74)	0.47 (0.71)	0.47 (0.80)	0.00
Total N distinct ICD9/ICD10 diagnoses at the 3rd digit level Copy	11.03 (11.87)	11.05 (12.50)	0.00	7.05 (9.40)	6.75 (9.53)	0.03	13.29 (12.56)	12.93 (13.09)	10.76 (11.43)	10.47 (11.86)	0.02
For PS											
Hemorrhagic stroke+Other cerebrovascular disease+Cerebrovascular procedure (for PS); n (%)	33 (1.5%)	29 (1.3%)	0.02	44 (0.8%)	39 (0.7%)	0.01	157 (1.9%)	172 (2.1%)	234 (1.5%)	240 (1.5%)	0.00
Major trauma potentially causing prolonged immobilization	173 (8.0%)	170 (7.9%)	#DIV/0!	379 (6.7%)	349 (6.1%)	#DIV/0!	559 (6.9%)	538 (6.7%)	379 (6.7%)	349 (6.1%)	0.02
Occurrence of creatinine tests ordered (for PS); n (%)	159 (7.4%)	154 (7.2%)	0.01	327 (5.8%)	314 (5.5%)	0.01	846 (10.5%)	782 (9.7%)	1332 (8.4%)	1250 (7.9%)	0.02
Occurrence of BUN tests ordered (for PS); n (%)	78 (3.6%)	76 (3.5%)	0.01	153 (2.7%)	169 (3.0%)	-0.02	407 (5.0%)	413 (5.1%)	638 (4.0%)	658 (4.1%)	-0.01
Occurrence of chronic renal insufficiency w/o CKD (for PS); n (%)	118 (5.5%)	122 (5.7%)	-0.01	142 (2.5%)	136 (2.4%)	0.01	464 (5.8%)	515 (6.4%)	724 (4.6%)	773 (4.9%)	-0.01
Chronic kidney disease Stage 1-2 (for PS); n (%)	52 (2.4%)	55 (2.6%)	-0.01	43 (0.8%)	49 (0.9%)	-0.01	129 (1.6%)	133 (1.6%)	224 (1.4%)	237 (1.5%)	-0.01
Chronic kidney disease Stage 3-6 (for PS); n (%)	154 (7.2%)	158 (7.3%)	0.00	121 (2.1%)	139 (2.4%)	-0.02	595 (7.4%)	649 (8.0%)	870 (5.5%)	946 (6.0%)	-0.02
Acute kidney injury; n (%)	238 (11.1%)	231 (10.7%)	#DIV/0!	350 (6.2%)	363 (6.4%)	#DIV/0!	824 (10.2%)	887 (11.0%)	350 (6.2%)	363 (6.4%)	-0.01
Bladder stones+Kidney stones (for PS); n (%)	87 (4.0%)	62 (2.9%)	0.06	167 (2.9%)	179 (3.2%)	-0.02	312 (3.9%)	275 (3.4%)	566 (3.6%)	516 (3.2%)	0.02
Alcohol abuse or dependence+Drug abuse or dependence (for PS); n (%)	131 (6.1%)	127 (5.9%)	0.01	220 (3.9%)	205 (3.6%)	0.02	186 (2.3%)	166 (2.1%)	537 (3.4%)	498 (3.1%)	0.02
Other atherosclerosis+Cardiac conduction disorders+Other CVD (for PS)v2 Copy; n (%)	668 (31.0%)	666 (30.9%)	0.00	1,387 (24.4%)	1,374 (24.2%)	0.00	2,499 (31.0%)	2,539 (31.5%)	4554 (28.7%)	4579 (28.8%)	0.00
Previous cardiac procedure (CABG or PTCA or Stent) + History of CABG or PTCA (for PS); n (%)	94 (4.4%)	92 (4.3%)	0.00	85 (1.5%)	77 (1.4%)	0.01	698 (8.7%)	736 (9.1%)	877 (5.5%)	905 (5.7%)	-0.01
Diabetes with complication; n (%)	194 (9.0%)	192 (8.9%)	#DIV/0!	246 (4.3%)	251 (4.4%)	#DIV/0!	611 (7.6%)	661 (8.2%)	246 (4.3%)	251 (4.4%)	0.00
Delirium + Psychosis (for PS); n (%)	112 (5.2%)	133 (6.2%)	-0.04	153 (2.7%)	137 (2.4%)	0.02	469 (5.8%)	463 (5.7%)	734 (4.6%)	733 (4.6%)	0.00
Any use of Meglitinides (for PS); n (%)	** (0.2%)	** (0.2%)	0.00	** (0.2%)	** (0.1%)	0.03	29 (0.4%)	24 (0.3%)	#VALUE!	#VALUE!	#VALUE!
Any use of GIGs (for PS); n (%)	** (0.0%)	** (0.0%)	#DIV/0!	** (0.0%)	** (0.1%)	-0.04	** (0.0%)	** (0.0%)	#VALUE!	#VALUE!	#VALUE!
CKD stage 3-6 + dialysis (for PS); n (%)	154 (7.2%)	159 (7.4%)	-0.01	121 (2.1%)	139 (2.4%)	-0.02	598 (7.4%)	651 (8.1%)	873 (5.5%)	949 (6.0%)	-0.02
Use of thiazide; n (%)	184 (8.5%)	197 (9.2%)	-0.02	388 (6.8%)	414 (7.3%)	-0.02	964 (12.0%)	1,010 (12.5%)	1536 (9.7%)	1621 (10.2%)	-0.02
Use of beta blockers; n (%)	517 (24.0%)	523 (24.3%)	-0.01	1,040 (18.3%)	1,072 (18.9%)	-0.02	2,759 (34.2%)	2,859 (35.4%)	4316 (27.2%)	4454 (28.0%)	-0.02
Use of calcium channel blockers; n (%)	392 (18.2%)	406 (18.9%)	-0.02	825 (14.5%)	832 (14.7%)	-0.01	2,170 (26.9%)	2,197 (27.2%)	3387 (21.3%)	3435 (21.6%)	-0.01
All antidiabetic medications except Insulin; n (%)	308 (14.3%)	331 (15.4%)	-0.03	650 (11.5%)	655 (11.5%)	0.00	1,245 (15.4%)	1,281 (15.9%)	2203 (13.9%)	2267 (14.3%)	-0.01
DM Medications -Insulin Copy; n (%)	109 (5.1%)	104 (4.8%)	0.01	219 (3.9%)	224 (3.9%)	0.00	276 (3.4%)	297 (3.7%)	604 (3.8%)	625 (3.9%)	-0.01
Use of Low Intensity Statins; n (%)	433 (20.1%)	458 (21.3%)	-0.03	804 (14.2%)	874 (15.4%)	-0.03	2,351 (29.2%)	2,398 (29.7%)	3588 (22.6%)	3730 (23.5%)	-0.02
Use of High Intensity Statins; n (%)	282 (13.1%)	285 (13.2%)	0.00	593 (10.4%)	540 (9.5%)	0.03	1,285 (15.9%)	1,313 (16.3%)	2160 (13.6%)	2138 (13.5%)	0.00
Malignant hypertension; n (%)	79 (3.7%)	123 (5.7%)	-0.09	1,702 (30.0%)	1,848 (32.6%)	-0.06	2,901 (36.0%)	3,205 (39.7%)	4682 (29.5%)	5176 (32.6%)	-0.07
Cardiovascular stress test; n (%)	17 (0.8%)	** (0.3%)	0.07	41 (0.7%)	27 (0.5%)	0.03	94 (1.2%)	97 (1.2%)	152 (1.0%)	#VALUE!	#VALUE!
Echocardiogram; n (%)	1,240 (57.6%)	1,203 (55.9%)	0.03	3,183 (56.1%)	3,236 (57.0%)	-0.02	4,635 (57.5%)	4,681 (58.0%)	9058 (57.0%)	9120 (57.4%)	-0.01
Number of BNP tests	0.11 (0.39)	0.12 (0.39)	-0.03	0.10 (0.36)	0.10 (0.35)	0.00	0.15 (0.41)	0.16 (0.44)	0.13 (0.39)	0.13 (0.40)	0.00
Number of Cardiac biomarkers tests (tropnin, CK-MBs, Myoglobin, CPK)	0.49 (1.92)	0.49 (1.37)	0.00	0.36 (1.04)	0.38 (1.28)	-0.02	0.30 (0.62)	0.32 (0.66)	0.35 (1.04)	0.36 (1.03)	0.00
Number of Ambulatory Blood pressure monitoring tests	0.00 (0.00)	0.00 (0.00)	#DIV/0!	0.00 (0.02)	0.00 (0.01)	0.00	0.00 (0.00)	0.00 (0.00)	0.00 (0.01)	0.00 (0.01)	0.00
N of days on antihypertensive medications during baseline	77.64 (79.51)	81.69 (80.51)	-0.05	62.17 (77.97)	63.02 (77.51)	-0.01	110.17 (77.59)	112.91 (76.57)	88.62 (77.99)	90.87 (77.45)	0.00
N of days in database anytime prior	1,744.50 (1,301.73)	1,772.23 (1,328.01)	-0.02	1,984.17 (1,373.99)	2,044.08 (1,376.43)	-0.04	638.67 (341.16)	621.10 (306.74)	1268.92 (981.16)	1285.15 (981.38)	0.00
Mean Copay for per prescription cost (charges in U.S. \$) (180-1 day prior)	22.68 (37.15)	21.62 (36.53)	0.03	14.31 (19.86)	14.46 (36.77)	-0.01	109.17 (121.45)	109.27 (115.41)	63.58 (88.39)	63.54 (86.16)	0.00
...Missing; n (%)	149 (6.9%)	137 (6.4%)	0.02	504 (8.9%)	484 (8.5%)	0.01	246 (3.1%)	247 (3.1%)	899 (5.7%)	868 (5.5%)	0.01

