5.1 Cohort Summary

This study will involve a new user, parallel group, propensity score-matched, retrospective cohort study design comparing rivaroxaban to warfarin users. The patients will be required to have continuous enrollment during a baseline period of 180 days before initiation of rivaroxaban or warfarin (index date). We will restrict the analyses to patients with a diagnosis of PE.

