Power	0.967396851

- MarketScan

Non-inferiority Analysis	
Number of patients matched	18,776
Reference	9,388
Exposed	9,388
Risk per 1,000 patients	14.88
Assumed HR from RCT	1.12
Alpha (2-sided)	0.05
Non-inferiority margin	2
Number of events expected	279.38688
Power	0.998048094

○ Medicare

Non-inferiority Analysis	
Number of patients matched	32,386
Reference	16,193
Exposed	16,193
Risk per 1,000 patients	13.64
Assumed HR from RCT	1.12
Alpha (2-sided)	0.05
Non-inferiority margin	2
Number of events expected	441.74504
Power	0.999982118

- Stop analyses until balance and final power assessment are reviewed by primary investigators, FDA, and assigned members of advisory board.

Reviewed by PI:		Date reviewed:	
Reviewed by FDA:		Date reviewed:	
Reasons for stopping analysis (if required):			

9. Balance Assessment

Action report links:

Optum: <https://bwh-dope.aetion.com/projects/details/1527/rwrs/67705>

Marketscan: <https://bwh-dope.aetion.com/projects/details/1653/rwrs/67706>

Medicare: <https://bwh-dope.aetion.com/projects/details/1525/rwrs/67894>

Date conducted: 3/28/2021

After review of initial feasibility and power analyses, complete creation of the remaining covariates from Section 6.2. Again, using the dummy outcome of a 90-day gap in database enrollment, complete a 1:1 PS-matched analysis. The PS should include the complete list of covariates.

- Provide plot of PS distributions stratified by treatment group.

Note- Please refer to **Appendix B**.

- Report covariate balance after matching.

Note- Please refer to **Appendix B**.

- Report reasons for censoring by treatment group.

	Overall	Referent	Exposure
Dummy outcome	0 (0.0%)	0 (0.0%)	0 (0.0%)
Death	477 (1.50%)	218 (1.37%)	259 (1.63%)
Start of an additional exposure	1,584 (4.98%)	1,023 (6.44 %)	561 (3.53%)
End of index exposure	23,632 (74.35%)	11,350 (71.42%)	12,282 (77.28%)
Specified date reached	1,617 (5.09%)	875 (5.51%)	742 (4.67%)
End of patient enrollment	2,079 (6.54%)	1,046 (6.58%)	1,033 (6.50%)
Switch to other NOACs (for censoring) + nursing home admission	2,397 (7.54%)	1,381 (8.69%)	1,016 (6.39%)

- Report follow-up time by treatment group.

Median Follow-Up Time (Days) [IQR]			
Patient Group	Optum	MarketScan	Medicare
Overall Patient Population	70 [36-174]	91 [38-184]	97 [38-195]
Referent	75 [38-173]	92 [40-178]	100 [41-199]
Exposure	65 [33-175]	91 [38-188]	88 [38-190]

10. Final Power Assessment

Date conducted: 03/28/2021

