Appendix A

Trial Name (with web links)	EINSTEIN PE
Trial Name (with pdf links)	EINSTEIN PE
NCT	NCT00439777
Therapeutic Area	Cardiology/Vascular Diseases
Study batch	NOACs
Brand Name	Xarelto
Generic Name	Rivaroxaban
Sponsor	Bayer Johnson & Johnson Pharmaceutical Research & Development, L.L.C
Year	2012
Measurable endpoint	Percentage of Participants With Symptomatic Recurrent Venous Thromboembolism [VTE] (i.e. the Composite of Recurrent Deep Vein Thrombosis [DVT] or Fatal or Non-fatal Pulmonary Embolism [PE]) Until the Intended End of Study Treatment
Exposure	Rivaroxaban
Comparator	Enoxaparin/VKA
Population	Patients of legal age who had acute symptomatic pulmonary embolism with or without deep-vein thrombosis
Trial finding	HR = 1.12 (95% CI 0.75 to 1.68)
No. of Patients	4,832 (2,419 in exposed arm)
Non-inferiority margin	HR = 2.0
Assay Sens. Endpoint (from trial)	Percentage of Participants With the Composite Variable Comprising Recurrent DVT, Non-fatal PE and All Cause Mortality Until the Intended End of Study Treatment
Finding for potential Assay Sens. Outcome from trial-	HR = 0.85 (95% CI 0.63 to 1.14)
Power	0.90. Assuming equal efficacy, a total of 88 events was calculated to give a power of 90% to prove that rivaroxaban is at least as effective as the comparator, considering a non-inferiority upper CI margin for the hazard ratio of 2.0 (two-sided $\alpha=0.05$). A mean incidence for the primary efficacy outcome of 3% was expected and an enrollment of at least 3000 patients was necessary

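### Matching equalises the mean of baseline hospital days but not their distribution (variance ratio 2.1 to 2.8), and the tabulated balance measure cannot show it

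*Combined protocol and SAP*

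**What the plan says.** Section 5.1 requires "continuous enrollment during a baseline period of 180 days before initiation of rivaroxaban or warfarin", and the baseline covariates come from that look-back. Section 9 tells the analyst to "complete a 1:1 PS-matched analysis" and adds: "The PS should include the complete list of covariates". So hospital days should be in the score, but the plan does not say in what functional form. For the check, Section 9 says only "Report covariate balance after matching" and points to Appendix B. It gives no threshold for the standardised difference and no criterion for spread.

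Appendix B prints "Number of hospital days" as mean (SD) per arm, before and after matching. Before matching, the standardised differences are 0.39, 0.41 and 0.40 (Optum, MarketScan, Medicare), with warfarin the longer by about 1.8 to 2.1 days. After matching, they are 0.02 in Optum, 0.01 in MarketScan and 0.01 pooled. No Medicare value is shown.

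**The concern.** Hospital days had one of the larger imbalances before matching and are a plausible marker of severity. Read by its standardised differences, the matched table says the imbalance is gone. The SDs in the same row say otherwise: the arms share a mean but not a distribution. If the risk of recurrent VTE or major bleeding bends with hospital days, for instance flat at low totals and steep at high ones, equal means do not remove confounding by this covariate. The hazard ratio would then carry some of it, and nothing in the planned balance report would flag it.

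**Working it through.** **Column order.** The Section 14.1 template lists the referent before the exposure. The matched heparin row in Optum confirms this: the first column has 243 users, more than the 209 in the whole rivaroxaban group before matching, so the first column is warfarin.

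**Step 1: reproduce the printed balance figures.** Standardised difference = (mean_W − mean_R) / √[(SD_W² + SD_R²)/2], with W warfarin and R rivaroxaban.

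| After matching | Warfarin | Rivaroxaban | Std. diff. recomputed | Printed |
|---|---|---|---|---|
| Optum | 5.88 (3.52) | 5.78 (5.88) | 0.10/4.85 = 0.021 | 0.02 |
| MarketScan | 5.05 (3.36) | 4.99 (4.88) | 0.06/4.19 = 0.014 | 0.01 |
| Medicare | 6.38 (3.73) | 6.32 (6.02) | 0.06/5.01 = 0.012 | none |
| Pooled | 5.84 (3.57) | 5.77 (5.62) | 0.07/4.71 = 0.015 | 0.01 |

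The printed values are right as comparisons of means. (Before matching, the pooled value is printed as 0.00 for 6.50 (5.43) vs 4.50 (4.48). It recomputes to 2.00/4.98 = 0.40 and should be corrected.)

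**Step 2: compare the spread.** Variance ratio = (SD_R / SD_W)².

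| | Before matching | After matching |
|---|---|---|
| Optum | (4.04/4.96)² = 0.66 | (5.88/3.52)² = 2.79 |
| MarketScan | (4.12/5.37)² = 0.59 | (4.88/3.36)² = 2.11 |
| Medicare | (4.84/5.61)² = 0.74 | (6.02/3.73)² = 2.60 |

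The ratio crosses 1 in the same direction in all three databases.

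**Step 3: who was left out.** With N and M the size and mean of a full group, and n and m those of its matched part, the unmatched mean is (N·M − n·m)/(N − n). Second moments give the SD in the same way. For Optum rivaroxaban, N = 776 + 5,672 = 6,448 (HbA1c results plus missing) and n = 2,153, so the mean is (6,448 × 4.14 − 2,153 × 5.78)/4,295 = 3.32. For Medicare I used n = 15,893 − 2,153 − 5,675 = 8,065, where 15,893 is the column total of the Section 9 censoring table. That count reproduces the pooled matched row; the 8,671 in Section 10 does not.

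- Unmatched rivaroxaban patients: mean 3.1 to 3.5 days, SD 2.3 to 2.4.
- Unmatched warfarin patients: mean 5.9 to 6.9 days, SD 5.3 to 6.1.

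Matching shed short-total rivaroxaban patients and widely spread warfarin patients. A score that is linear in hospital days could do this, but the form used is not documented.

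**Step 4: is it general?** No. Matched variance ratios are 1.04 to 1.14 for the comorbidity index, 0.92 to 1.00 for office visits and 0.85 to 1.27 for number of hospitalisations. The count of brand-name drugs does fail, the other way: (3.34/5.57)² = 0.36, (3.38/5.19)² = 0.42 and (3.75/5.67)² = 0.44.

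**Step 5: what the spread implies.** The documents give no quantiles, so this step assumes a shape fitted to the pooled matched mean and SD.

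| Rivaroxaban vs warfarin | Gamma | Log-normal |
|---|---|---|
| 2 days or fewer | 28% vs 10% | 19% vs 5% |
| More than 14 days | 8.5% vs 3.1% | 6.8% vs 3.3% |

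Both tails are heavier in the rivaroxaban arm.

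**The case against.** The strongest reply is that unequal variance is not bias. If risk is roughly linear in hospital days, equal means leave little confounding. Several other severity markers agree after matching in mean and spread (pooled, warfarin vs rivaroxaban): comorbidity index 2.30 (2.22) vs 2.26 (2.28), HAS-BLED 2.93 (0.91) vs 2.94 (0.89), hospitalisations 1.21 (0.64) vs 1.22 (0.62). Any effect may also be small. Suppose, purely as an assumption, that more than 14 days doubled the hazard and the short-total excess is ignored. The hazard ratio would then move by about 2% (MarketScan log-normal, 1.048/1.023) to 6% (Optum gamma, 1.091/1.030), little against a margin of 2.0. The SDs are printed, so nothing is hidden. All of this stands, and it limits the point to a diagnostic and a respecification. It does not show that risk is linear, and it leaves the check blind to spread.

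A reader might be tempted to go further in four ways that the documents do not support.

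- *Two to three times as many very long stays on rivaroxaban.* No count or cutoff is given. Across five assumed shapes and three databases, the model-based ratio is 1.5 to 2.2 at 12 days, 1.9 to 3.5 at 14 and 3.9 to 43 at 21. Rare outliers of 60 to 90 days in about 0.3 to 0.6% of the pooled rivaroxaban arm could also produce the extra variance. The row appears to sum days over the baseline window rather than measure single stays.
- *Warfarin start-up as the cause of the pre-match gap.* Optum heparin use of 53.4% vs 3.3% before matching is compatible with this, but no section says so. "Enoxaparin/VKA" in Appendix A describes the trial's comparator; this study's is warfarin.
- *Bias against rivaroxaban.* The same models give a larger excess of short totals, in percentage points, than of long ones. Matched deaths (259 vs 218) give z = 41/√477 = 1.88, from crude counts under unequal censoring. Prior cancer runs the other way (14.7% rivaroxaban vs 15.9% warfarin).
- *The balance review was passed.* Section 9 sets no threshold, and the document records no review outcome.

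**Conclusion.** The point holds as a gap in the balance assessment. After matching, hospital days have 2.79, 2.11 and 2.60 times the variance in the rivaroxaban arm in Optum, MarketScan and Medicare, reversed from 0.66, 0.59 and 0.74, while the mean-only measure reads 0.01 to 0.02. This rests only on printed SDs and the confirmed column order. That both tails are heavier rests on an assumed skewed shape. Residual confounding is possible where risk is non-linear in hospital days; its sign and size cannot be settled from the documents. Brand-name drug count shows that the gap in the check is not confined to one row. The change is worth making because it is cheap and the comparative analyses in Section 13 are still blank.

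**What to change.** Before the comparative analyses are run:

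1. State how hospital days and the brand-name drug count enter the propensity score. Enter both as categories or a spline, then re-match in each database.
2. In the Section 9 balance assessment, add a variance-ratio column beside the standardised difference for every continuous covariate, with a flag stated in advance. Values outside 0.5 to 2 are one convention; it is not taken from the documents, and MarketScan at 2.11 only just exceeds it.
3. Report quantiles of hospital days by arm, before and after matching, and print the missing Medicare standardised differences.

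The cost is a re-run on data already in hand and possibly fewer pairs. With pooled power at 0.99999, that loss matters little overall. Optum alone has 0.59 and would lose more. If the re-matched ratios remain outside the flag, say so beside the result.
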